7.1 Sample Size Determination

Data analysis: Assuming a medium effect size (0.3) and a target power of 80%, a two-armed study would need about 108 subjects and a single arm about 88 subjects. Due to the costs associated with a study, we propose a single armed study of 12 subjects with corollary science including RNA sequencing. This will reduce costs and provide biomarkers predictive of response. Effect sizes will be estimated for the appropriate statistical tests that will be used for group comparisons in future studies. This will enable more accurate power and sample size estimates moving forward.

7.2 Statistical Methods

Descriptive Statistics

Sample Size Computation and Power Analysis:

The sample size for this pilot study is set at 12 subjects for logistical and financial reasons. This is similar in size to other exploratory studies and will provide adequate data for estimation purposes for planning future studies. With 12 subjects, the study is intended to be for estimation purposes only.

Statistical Analysis Plan:

Data Analysis - The statistical analysis will provide descriptive summary statistics for categorical and continuous outcomes. Categorical variables will be described by their count and proportion of occurrence while continuous, normally distributed variables will be described by their mean and standard deviation; and continuous, non-normally distributed variables will be described by their median and range. The paired or unpaired Wilcoxon tests will be used to quantify differences in numerical outcomes while the Fisher's exact test and the McNemar's or Bowker's tests will be used to quantify changes in categorical variables. If missingness occurs at random a mixed model will be utilized to assess the change in the lesion over time. A sensitivity analysis will be performed using the last observation carried forward and the results will be compared to that of the mixed model.

Effect sizes will be estimated for the appropriate statistical tests that will be used for group comparisons in future studies. This will enable more accurate power and sample size estimates moving forward.

Bioinformatic Analysis:

Bulk RNA-seq analysis: We will use our recently developed LinNorm program

(https://www.bioconductor.org/packages/release/bioc/html/Linnorm.html) to process RNA-seq data and detect differentially expressed genes (DEGs) by comparing the RNA-seq profiles. We will first find DEG between responsive and non-responsive samples from the same individual by using paired or unpaired Wilcoxon ranksum test (depending on how the samples are collected). We will then rank each gene in the DEGs based on the occurrence frequencies in all 12 subjects to find common DEGs for responsiveness (use permutation test to determine the p value). For the top ranked genes (common DEGs), we will use DAVID¹¹ and GSEA¹² software to find enriched inflammatory pathways and GO terms for the DEGs. By comparing the normal tissue with the pathogenic tissue (responsive + non-responsible) using the above approach, we will detect a common DEGs for LP pathogenesis. Hierarchical clustering¹³ and Principal Component Analysis (PCA)¹⁴ will be applied to samples for their hierarchical relationship and clustering properties. Ideally normal, responsive and non-responsible tissues should form three distinct groups. The PCA analysis will provide us a set of gene signatures that can distinguish these three types of tissues. The common DEGs for responsiveness and pathogenesis, as well as gene signature from PCA will be used for our pathogenesis or survival prediction. We will perform structure variants calling from RNA-seq data with SNPiR, 15 and reconstruct gene co-expression networks with ARACHNE. 16 Additionally, we will perform de-convolutional analysis, to compare the immune profiles of responsive and non-responsive tissue and to correlate immune profiles. Predictive biomarkers will be correlated with lesional and global responses.

Single-cell RNA Seq analysis: will be performed according to standard operating procedures of University of Michigan genomics lab and bioinformatics

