week 0 and 2. Blood collection will include the isolation at week 0, 1, 2, 3, 4, 8, 12, 16, 20, 24, 28, and 32. Blood will be drawn into 5mL vials and subsequently separated. The serum and cell pellet will be stored for future analysis. At weeks 0 and 2, an additional 5mL vial of blood will be drawn from patients who agree to provide single-cell RNA sequencing samples. For these samples, the buffy coat (containing peripheral blood mononuclear cells, PBMCs) will be isolated from whole blood, then immediately placed into cryopreservation medium and stored in a -80°C biobank freezer. Up to five skin biopsies will be taken during the study for all patients. At week 0, up to two, 3mm tissue biopsies will be taken from LP lesional skin and one biopsy will be taken from normal appearing skin for bulk RNA sequencing. The initial biopsy of lesional tissue and control will be annotated. At week 2, up to two, 3mm biopsies will be taken – one from normal appearing skin, one from lesional responsive tissue, and/or one from lesional non-responsive tissue. An additional two, 6-8mm biopsies of lesional tissue for single-cell RNA sequencing will be taken—one at week 0 and one at week 2 from patients who opt in. The week 2 biopsy will be obtained from an annotated lesion, whether responsive or non-responsive. Responsive and non-responsive lesions will be determined by the change in mCAILS between week 0 and 2. Responsive tissue will require at least 50% reduction in mCAILS while non-responsive tissue can have progression, no change, or up to a 50% reduction in mCAILS. The lesions will be chosen utilizing full body photographs taken previously at week 0. Up to 60 of the 3mm biopsy samples will be snap frozen and stored in the tissue biobank. Once completed, RNA sequencing will be performed on the tissue samples and analysis will be performed. Paired analysis of treatment responsive and refractory lesions will be made as well as treated and untreated lesions.

Tissue will be collected for bulk RNA sequencing and single cell RNA sequencing (for patients who opt in) at

Nucleic Acid Extractions: RNA will be extracted from a total of 50 µm of fresh tissue using the Qiagen FFPE RNeasy Micro extraction Kit according to manufacturer's recommendation.

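### The within-patient Wilcoxon step for bulk RNA-seq cannot separate genes with one responsive and one non-responsive week-2 sample, and no workable calling rule is stated

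*Combined protocol and SAP*

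**What the plan says.** The bulk RNA-seq plan in section 7.2 (Bioinformatic Analysis) first names software: "We will use our recently developed LinNorm program" (a package link follows) "to process RNA-seq data and detect differentially expressed genes (DEGs) by comparing the RNA-seq profiles". The only test it names for this step comes next: "We will first find DEG between responsive and non-responsive samples from the same individual by using paired or unpaired Wilcoxon ranksum test". The choice between paired and unpaired is left to how the samples are obtained. Then: "We will then rank each gene in the DEGs based on the occurrence frequencies in all 12 subjects", with a permutation p-value attached to that ranking. The top genes go to DAVID and GSEA.

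Diseased tissue follows the same route: "By comparing the normal tissue with the pathogenic tissue (responsive + non-responsible) using the above approach". Later uses are: "The common DEGs for responsiveness and pathogenesis, as well as gene signature from PCA will be used for our pathogenesis or survival prediction", and "Predictive biomarkers will be correlated with lesional and global responses". No significance level, sidedness, fold-change or false discovery rate (FDR) is given for calling a gene within a patient.

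The sampling is set out in section 3.1 and the visit list. Day 0 allows up to three 3 mm samples: up to two lesional and one normal. Week 2 (Visit 4) allows up to two, although section 3.1 lists three tissue types for that visit: "one from normal appearing skin, one from lesional responsive tissue, and/or one from lesional non-responsive tissue". The larger opt-in biopsies are for single-cell sequencing and add no bulk replicates. A lesion's response status comes from its change in mCAILS between weeks 0 and 2. Section 3.1 also announces a paired comparison of responsive and refractory lesions, without saying whether pairs are pooled across patients.

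**The concern.** A frequency over subjects needs one gene list per subject, so the text implies a separate Wilcoxon test in each patient. A rank test on one or two observations per group has very few attainable p-values. With one observation per group it has only one.

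The common-DEG ranking, its permutation test and the DAVID/GSEA step all take these lists as input. So do the DEG-based part of the prediction and any correlation of DEG-derived biomarkers with response. Someone following the text would have to report no DEGs or choose a cut-off after seeing the data. Section 7.1 gives biomarkers predictive of response as part of the reason for a 12-subject single-arm study, so this output matters even though the objective is exploratory.

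**Working it through.** **1. Samples per patient.** Three 3 mm samples at Day 0 plus two at week 2 make five. 12 x 5 = 60, which matches the maximum of 60 samples in section 3.1.

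**2. Possible groups within one patient.**
- Week 2 only: 1 responsive v 1 non-responsive, or no pair if one sample is normal skin.
- Week-0 lesions relabelled by later response, with both week-2 samples lesional: four lesional samples, split 2 v 2 or 3 v 1.
- Normal v lesional: 2 v 3 if normal skin is sampled at both visits, 1 v 4 if only at Day 0.

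**3. Smallest attainable p-value.** For groups of m and n without ties, the exact two-sided rank-sum floor is min(1, 2/C(m+n, m)). For k pairs, the signed-rank floor is 2/2^k.

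| Contrast | Split | Exact two-sided floor | Uncorrected normal, two-sided |
|---|---|---|---|
| Responsive v non-responsive, week 2 | 1 v 1 | 2/2 = 1.00 | 0.317 |
| Same, week 0 relabelled | 2 v 2 | 2/6 = 0.33 | 0.121 |
| Same, week 0 relabelled | 3 v 1 | 2/4 = 0.50 | 0.180 |
| Normal v lesional | 2 v 3 | 2/10 = 0.20 | 0.083 |
| Normal v lesional | 1 v 4 | 2/5 = 0.40 | 0.157 |

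At 1 v 1 the tabled value is the only one attainable, so all genes tie. The paired version gives the same exact result: 2/2^1 = 1.0. One-sided, the exact 1 v 1 floor is 0.5. At 2 v 3 the one-sided floor is 1/10 = 0.10 exact and 0.042 by uncorrected normal approximation. No split of five samples has an exact two-sided floor below 0.20.

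**4. What a cut-off at the floor would do.** Without ties, the share of non-differential genes called in a patient equals the floor: 100% at 1 v 1, 33% at 2 v 2, 50% at 3 v 1, 20% at 2 v 3 and 40% at 1 v 4. These are per-patient call rates. Assume 12 independent patients, all with the same split. The chance that a null gene is called in at least c of them is the sum over k from c to 12 of C(12,k) r^k (1-r)^(12-k):
- r = 0.20 (2 v 3), c = 7: 0.0039.
- r = 1/3 (2 v 2), c = 10: 0.0005.
- r = 1 (1 v 1): every gene is called in all 12, so there is nothing to rank.

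**5. The same tissue tested across patients.** The exact two-sided signed-rank floor is 2/2^12 = 0.00049 with 12 complete pairs, 2/2^8 = 0.0078 with 8 and 2/2^6 = 0.031 with 6. The documents give no gene count. Assuming 10,000 to 25,000 genes, Benjamini-Hochberg at 5% with 12 pairs needs about 98 to 245 genes at the floor (genes x 0.00049/0.05).

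**The case against.** The strongest reply is that the plan's only p-value belongs to the frequency ranking, and the within-patient step merely feeds a count. A loose call in each patient is harmless if the permutation null allows for it, as step 4 shows. This stands for splits other than 1 v 1, so a reader should not take 20% to 50% as final error rates. It does not help at 1 v 1, where all genes have the same count. Counting concordant direction over 12 pairs could reach 2/2^12 = 0.00049, but the plan does not say that direction is counted.

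Second, the plan states neither exactness nor sidedness. A reader might infer that no conventional cut-off can be met under any version of the test. The documents do not support that: the uncorrected normal value at 2 v 3 is 0.083 two-sided and 0.042 one-sided. The plan specifies neither, however, and a normal approximation on five observations is hard to defend. At 1 v 1 no version separates genes at a conventional level.

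Third, LinNorm is named for detecting DEGs. That is fair, but the documents state no model or threshold for it.

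Fourth, the paired comparison in section 3.1 could mean an across-patient test, which would work at nominal levels. But section 7.2 ties the test to one individual and then counts over subjects, so the text needs to be settled.

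**Conclusion.** The step fails when followed as written. With week-2 samples alone, the exact two-sided p-value is 1.0 for every gene in every patient. With relabelled week-0 lesions the exact two-sided floors are 0.33 or 0.50, and for normal against lesional tissue 0.20 or 0.40. For these larger splits the frequency count could be made usable, but the plan gives no rule for doing so.

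This rests on reading section 7.2 as one test per patient, on the cap of two 3 mm samples at week 2, and on no ties. It should be fixed, but it concerns the exploratory objective only. A reader might infer that the whole transcriptomic programme, or the trial itself, is compromised. The documents do not support that. PCA, clustering and deconvolution do not use the per-patient lists. The week-16 PGA endpoint, the secondary endpoints and safety are untouched.

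**What to change.** Replace the within-individual test and frequency ranking in section 7.2 with one gene-wise analysis across patients, for example a linear model such as limma-voom, with patient as a block or random effect.

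- **Tissue-by-time levels:** week-0 normal, week-0 lesional, week-2 normal, week-2 responsive and week-2 non-responsive. Untreated and treated normal skin stay separate. At full sampling a blocked model leaves 60 - 12 - 4 = 44 residual degrees of freedom, fewer if biopsies are missing.
- **Linked samples:** where week-0 and week-2 samples come from the same annotated lesion, account for that link.
- **Prediction from week 0:** where week-0 lesions can be linked to later response, split that level by response. Part of this contrast lies between patients, so use a random patient effect and treat the patient as the unit.
- **Rules to state:** the DEG threshold and FDR level; permutation of labels only within patient for within-patient contrasts; the part LinNorm plays; and that the paired comparison in section 3.1 is this analysis.
- **Downstream use:** take the resulting list into DAVID/GSEA and the biomarker correlations.
- **Sampling text:** reconcile the three week-2 tissue types listed in section 3.1 with the cap of two, without adding biopsies.

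A pooled signed-rank test is a weaker alternative because of the floors in step 5.

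The cost is SAP wording and a little more analysis work, with no extra visits. The linear model brings parametric assumptions. The documents do not show whether sequencing data have already been analysed; if they have, label the change post hoc.

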Appendix:

Physician Global Assessment: 17, 18

Grade 0 Completely clear: no evidence of disease (100% improvement) CCR

Grade 1 Almost clear: very significant clearance (≥90% to <100%) PR

Grade 2 Marked Improvement: significant improvement (≥75% to <90%) PR

Grade 3 Moderate improvement: intermediate between slight and marked (≥50% to <75%) PR

Grade 4 Slight improvement: some improvement (≥25% to <50%); however, significant evidence of disease remains SD

Grade 5 No change; disease has not changed from baseline condition (+/-<25%) SD

Grade 6 Worse, disease is worse than at baseline evaluation by (≥25%) or more PD

CCR- Complete clinical response

PR- Partial response

SD- Stable disease

PD- Progressive Disease

Modified CAILS-

Clinical Assessment Scale of Severity for Index Lesion Signs and Symptoms (mCAILS) 17,18

Scale Grade

- 0 No evidence of sign or symptom
- 1 Intermediate interval
- 2 Mild: less than average presentation of sign or symptom
- 3 Intermediate interval
- 4 Moderate: average disease presentation of sign or symptom
- 5 Intermediate interval
- 6 Severe: greater than 25% worse than average severity of sign or symptom
- 7 Intermediate interval
- 8 Very severe: the near worst severity sign or symptom

A scale of 0 to 18 was used to grade lesion size by square centimeter (0, 0 [no measurable area]; 1, >0 and \leq 4; 2, >4 and \leq 10; 3, >10 and \leq 16; 4, >16 and \leq 25; 5, >25 and \leq 35; 6, >35 and \leq 45; 7, >45 and \leq 55; 8, >55 and \leq 70; 9, >70 and \leq 90; 10, >90 and \leq 110; 11, >110 and \leq 130; 12, >130 and \leq 15; 13, >155 and \leq 180; 14, >180 and \leq 210; 15, >210 and \leq 240; 16, >240 and \leq 270; 17, >270 and \leq 300; and 18, >300). The area of the lesion will be measured with digital planimetry. 17-19

mCAILS index lesion score:

- 1. Erythema (0-8)
- 2. Scaling (0-8)
- 3. Plaque elevation (0-8)
- 4. Size (0-18)
- o Trained clinical evaluators assessed the same patients throughout the study.
- o The CA (the ratio of summation (Σ) of all clinical signs for these index lesion at each visit compared with baseline) included cutaneous tumors and all extra cutaneous manifestations of disease.
- o Complete clinical remission (CCR) required a CA ratio of 0 with no evidence of disease
- o Partial remission (PR) was defined as a CA ratio of 0.5 or lower
- o Progressive disease was defined as a 25% or higher increase in CA ratio (Olsen et al., 2011b, Duvic et al., 2001b)

Itch-

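### The lead RNA-seq response analysis compares tissue classes cut at 50% mCAILS reduction within each patient, where a Wilcoxon test cannot go below p = 1.0, and the measured degree of change is not modelled

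*Combined protocol and SAP*

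**What the plan says.** Section 3.1 bases lesion response on a measured quantity: "Responsive and non-responsive lesions will be determined by the change in mCAILS between week 0 and 2". It then splits that quantity in two: "Responsive tissue will require at least 50% reduction in mCAILS while non-responsive tissue can have progression, no change, or up to a 50% reduction". At Week 2 it allows up to two 3 mm bulk biopsies per patient, described as "one from normal appearing skin, one from lesional responsive tissue, and/or one from lesional non-responsive tissue".

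Section 7.2 makes the class contrast the first step of gene selection: "We will first find DEG between responsive and non-responsive samples from the same individual by using paired or unpaired Wilcoxon ranksum test". Next it will "rank each gene in the DEGs based on the occurrence frequencies in all 12 subjects", with a permutation p value. Pathway enrichment and the prediction signature draw on the resulting genes. A last sentence adds: "Predictive biomarkers will be correlated with lesional and global responses". The scale of response for that correlation is not given, and no model on continuous mCAILS change is specified.

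The Appendix holds the only visible precedent for the cut: "Partial remission (PR) was defined as a CA ratio of 0.5 or lower". Supplemental 1 says that the scale was devised for cutaneous T-cell lymphoma lesions and that no skin score is validated for LP.

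**The concern.** Two things are wrong, and the first is the more serious.

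The comparison is described as one made inside each individual, with gene frequencies then counted over the 12 subjects. With one sample per class per patient, no Wilcoxon test can flag a gene in any patient, so the frequency ranking has nothing to rank.

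The cut also discards degree of response. A lesion that worsened and one that improved by 49% count as the same tissue, and so do improvements of 51% and 100%. A patient whose lesions all fall in one class gives no within-patient contrast in this step.

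This matters because Section 7.1 accepts 12 uncontrolled patients, rather than about 88, partly on the ground that RNA sequencing will yield markers that predict response. Genes that follow degree of improvement are the ones that this step is most likely to miss.

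**Working it through.** **Inputs from the documents.** 12 patients; 4 lesions required and 8 preferred; 50% lesion response rate at Week 2 (all Section 3.1); at most one responsive and one non-responsive Week 2 bulk sample per patient (Section 3.1); mCAILS range 8 + 8 + 8 + 18 = 42 points (Appendix).

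**The plan's own figure.** Section 3.1 gives a chance below 1% that all 8 lesions resolve. At a 50% rate, 0.5^8 = 0.39%, so it reproduces. The documents state no power for the RNA-seq analysis.

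**Step 1: the test within one patient.** Rank-sum, 1 v 1: there are 2 orderings, so the smallest two-sided p is 2/2 = 1.0. Signed-rank on one pair: there are 2 sign patterns, and again p = 1.0. Even two samples per class would give 2/6 = 0.33. Pooled over n patients with a pair, the signed-rank floor is 2/2^n: 0.0625 for 5 pairs, 0.031 for 6 and 0.0005 for 12. Pooling is therefore essential, and at least 6 pairs are needed to reach 0.05.

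**Step 2: sensitivity of the class.** From a baseline of 13, a 6-point fall is 6/13 = 46% (non-responsive) and a 7-point fall is 7/13 = 54% (responsive).

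**Step 3: patients with lesions in one class.** With independent lesions at a 50% rate, the probability is 2 × 0.5^k for k lesions.
- 8 lesions: 0.8% each, or 12 × 0.0078 = 0.1 patients.
- 4 lesions: 12.5% each, or 12 × 0.125 = 1.5 patients.
- If lesions within a patient respond alike (beta-binomial, assumed intraclass correlation 0.4): 29%, or 3.4 patients, with 8 lesions; 46%, or 5.5 patients, with 4.

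**Step 4: power lost to the cut once pairs are pooled.** The documents give none of the following assumptions. Percent reduction has mean 50 and SD 25, capped at 100. Expression rises by 0.8 to 1.2 residual SD per SD of mCAILS change. Within-patient correlation is 0 to 0.5. Alpha is 0.05 two-sided and unadjusted. One lesion of each class is drawn at random. Both methods see the same discordant pairs. The continuous method regresses the paired expression difference on the paired mCAILS difference, through the origin.

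| Setting | Signed-rank | Paired t | Regression |
|---|---|---|---|
| 4 lesions, correlation 0.5, slope 1.2 | 42% | 52% | 68% |
| 8 lesions, correlation 0.5, slope 1.2 | 64% | 69% | 82% |
| 8 lesions, independent, slope 1.2 | 91% | 95% | 99% |

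Against signed-rank the gap runs from 99 − 91 = 8 to 68 − 42 = 26 points. Part of that is rank test v parametric test. Paired t v regression isolates the cut: 99 − 95 = 4, 82 − 69 = 13 and 68 − 52 = 16, or about 5 to 15 over all settings. Monte Carlo error with 1,200 replicates is about √(0.25/1200) = 1.4 points per figure.

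**Step 5: two changes of assumption.** If the most extreme lesion of each class is biopsied, the like-for-like loss is 0 to about 10 points. If expression jumps only at the 50% line, the class test wins, by about 3 to 20 points in the runs made.

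**The case against.** The strongest reply is that the design is deliberate. Comparing responsive with non-responsive tissue from one patient removes between-patient variation. The objective is exploratory, and Section 7.2 limits the study to estimation. If staff biopsy the clearest examples of each class, the cut costs little. The option of a paired or unpaired test may also mean that pooling over patients was intended. All of this is fair: it supports keeping the sampling rule and limits the size of the loss. It does not rescue the test as written, which is placed within the individual and precedes the count over subjects. Section 7.2 also names a software package for detecting genes, but the test that it states is the Wilcoxon.

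Three stronger readings are tempting and not supported.

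- A reader might infer a loss of 40 points or more. At 4 lesions, correlation 0.5 and slope 1.2, signed-rank has 42% power and a regression on all 12 patients 84%. That regression needs a second Week 2 lesion of the same class from patients without a pair, and Section 3.1 does not provide for one. It also mixes the cost of the cut with the choice of a rank test.
- A reader might infer that patients with lesions in one class are dropped from the study's biology. They lack a contrast in this step only. Their samples can still enter the comparison with normal skin, the clustering, the principal components and the correlation step.
- A reader might infer that the final correlation is confined to genes that passed the class test. Section 7.2 states no such gate. Nor does it say that the correlation uses the continuous score or recovers missed genes.

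**Conclusion.** The point holds in two parts. First, read literally, the within-individual Wilcoxon test cannot identify any gene, because its smallest two-sided p is 1.0. This follows from the biopsy counts and needs no assumption beyond reading Section 7.2 as written, with Week 2 tissue as the samples. Second, with pairs pooled, cutting mCAILS change at 50% costs power if expression follows degree of improvement: about 8 to 26 points against signed-rank and about 5 to 15 like for like. These sizes depend on the assumed SD, slope, correlation and alpha, and on random choice of lesions within class. They are illustrations and not properties of the plan. Between 0.1 and 1.5 of 12 patients lack a contrast if lesions are independent, and more if lesions within a patient respond alike. The primary endpoint is not affected. The biomarker aim is, and it is part of the case for a study of this size.

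**What to change.** In Section 7.2, make the lead response analysis a per-gene model pooled over patients. Regress normalised expression of each Week 2 lesional sample on that lesion's percent mCAILS change from Week 0, kept continuous. Include patient as a random effect, so that patients with one lesional sample still contribute between-patient information. Rank genes by the slope, with the false discovery rate controlled. If only one lesional sample per patient is available, use Spearman correlation with percent mCAILS change.

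Keep the 50% rule for choosing which lesions to biopsy and as a labelled supportive analysis, also pooled over patients. State the scale of response used in the final correlation step.

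The cost is SAP wording and a little analysis time; no samples, visits or patients are added. The sampling is unchanged, so the new model does not create pairs in patients who lack them. The downside is slightly lower sensitivity for genes that switch only at the 50% line, which the supportive analysis covers.

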3.2 Number of Subjects

12 subjects will be enrolled in this study.

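### Genes selected on lesion response in all 12 subjects are then used for prediction without any held-out test, so the planned analysis cannot show that they predict response

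*Combined protocol and SAP*

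**What the plan says.** Section 3.1 labels tissue at lesion level. A lesion is responsive if its mCAILS falls by at least 50% from week 0 to week 2, and otherwise non-responsive. Section 7.2 (Bioinformatic Analysis) then proceeds as follows.

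- First comparison: "We will first find DEG between responsive and non-responsive samples from the same individual by using paired or unpaired Wilcoxon ranksum test".
- Pooling over subjects: "rank each gene in the DEGs based on the occurrence frequencies in all 12 subjects to find common DEGs for responsiveness (use permutation test", with that test supplying the p value.
- PCA and hierarchical clustering are applied to the samples: "The PCA analysis will provide us a set of gene signatures that can distinguish these three types of tissues".
- Use: "The common DEGs for responsiveness and pathogenesis, as well as gene signature from PCA will be used for our pathogenesis or survival prediction".
- Follow-on: "Predictive biomarkers will be correlated with lesional and global responses".

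Section 3.2 fixes the pool: "12 subjects will be enrolled in this study". Section 7.1 gives 88 subjects for a single arm at 80% power, then proposes 12 on grounds of cost and says that the study will "provide biomarkers predictive of response". Section 2 lists the sequencing work as exploratory, and Section 7.2 describes the whole study as being for estimation.

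**The concern.** The response label is used twice: once to choose the genes and again when those genes are related to lesional response. With thousands of candidate genes and 12 subjects, some genes will line up with the label by chance, and choosing the best of them ensures that the chosen set looks good in the samples that chose it. All 12 subjects feed the selection and no other cohort is named, so nobody is left on whom the signature could fail.

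What is at stake is one of the benefits that Section 7.1 gives for a 12-subject study. A strong correlation with lesional response would be reported whether or not the genes carry any information. A later study could then be built on a signature that is noise. The primary endpoint is not affected.

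**Working it through.** **Inputs.** Subjects: 12 (3.2). Week 2 bulk samples: at most two 3 mm biopsies per subject (3.1). Label: lesion mCAILS change, week 0 to 2 (3.1). The number of genes tested and the split of the labels are not stated; I assume 1,000 to 20,000 genes and splits of 3/9, 4/8 and 6/6.

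**1. The plan's own figures.** Section 7.1 gives 88 and 108 at effect size 0.3 and 80% power. With two-sided alpha 0.05 (assumed), ((1.960 + 0.842)/0.3)² = 87.2, so 88. A chi-square test with w = 0.3 and 2 degrees of freedom gives 107.1, so 108. Both reproduce. Neither concerns the gene signatures, for which the plan gives no figure.

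**2. The within-subject step.** With at most one responsive and one non-responsive sample per subject at week 2, the smallest two-sided Wilcoxon p value within one subject is 1.0. Selection therefore has to be made across subjects, as the ranking over all 12 implies.

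**3. Single genes under no signal.** For one lesion per subject split n₁ against 12 − n₁, a null gene separates the two kinds completely with probability p = 2/C(12, n₁). For m lesion pairs all changing in the same direction, p = 2 × 0.5^m. The expected number of such genes is G × p.

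| Layout | p per gene | G = 1,000 | G = 20,000 |
|---|---|---|---|
| 6 vs 6 | 2/924 = 0.00216 | 2.2 | 43.3 |
| 4 vs 8 | 2/495 = 0.00404 | 4.0 | 80.8 |
| 3 vs 9 | 2/220 = 0.00909 | 9.1 | 181.8 |
| 12 pairs | 2 × 0.5¹² = 0.00049 | 0.5 | 9.8 |
| 6 pairs | 2 × 0.5⁶ = 0.03125 | 31 | 625 |

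For independent genes, the chance of at least one such gene, 1 − (1 − p)^G, is 0.89 or more in the unpaired layouts. With 12 pairs it runs from 0.39 to above 0.999.

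**4. Multi-gene signatures under no signal.** Genes were ranked by t statistic, the top 10 or 50 kept, and their values summed with the sign of the difference.

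- Scored in the same 12 subjects, AUC was 1.00 in 100% of runs. This held for 1,000 and 20,000 genes, all three splits, and genes either independent or correlated at 0.5 in blocks.
- With 6 or 12 lesion pairs, which is closer to the plan's layout, every pair was correctly ordered in 100% of runs.
- The top-50 signature scored in new, independent samples had AUC 0.49 to 0.51.
- Leave-one-out with genes reselected in each fold gave balanced accuracy 0.32 to 0.50. Values below 0.5 reflect the known downward bias of leave-one-out when there is no signal.

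**5. PCA without the label.** On all genes with no signal, PC1 alone separated the groups perfectly in 0.2 to 0.6% of runs, and PC1–2 in 0.2 to 1.8% (apparent AUC about 0.72). When more components were fitted to the label, perfect separation rose to 17 to 21% with PC1–5 and 94 to 96% with PC1–10.

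**6. The permutation test.** As written, it gives a p value for how often a gene recurs among subjects' DEG lists. It does not re-run selection and scoring together, so it does not correct the apparent performance of the selected set. No false-discovery control is stated.

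**The case against.** The sequencing objective is exploratory, the study is for estimation, and no classifier, accuracy, AUC or cut-off is named. That the signature will be scored in its own derivation samples is inferred from the absence of any other cohort. The plan also names a permutation test, which is a real safeguard for the gene list. All of this is fair, and it limits the point to an exploratory objective. It does not remove the point. Prediction is a stated aim, 7.1 offers predictive biomarkers as a benefit of the design, and an estimate obtained by scoring genes in the samples that selected them is biased whatever the study is called.

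Three stronger readings are tempting, and the documents do not support them.

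- A reader might infer that every planned signature, PCA included, will separate the groups perfectly by chance. Section 7.2 applies PCA to the samples and does not say that it is run on response-selected genes. Unsupervised leading components rarely separate perfectly (step 5).
- A reader might infer that responder patients are being separated. The selection labels are week 2 lesions. Patient-level response enters only through the later correlation with global measures (PGA, BSA, lesion count). These are not the selection label, so that correlation is unvalidated but not circular in the same direct way, and its bias was not calculated.
- A reader might infer that survival is not recorded at all. Section 8.3.1 mentions a death/survival case report form. What can be said is that Sections 3.4 and 3.5 define no survival endpoint.

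**Conclusion.** The concern holds for signatures built from label-selected DEGs. Following the plan as written makes their correlation with lesional response circular. With no true signal, apparent AUC is 1.00 and true AUC about 0.50, so good apparent performance in these 12 subjects would carry no information about prediction. PCA shares the problem only if it is run on the selected genes or its components are picked because they separate the groups; Section 7.2 leaves both open.

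The result rests on an assumed 1,000 to 20,000 genes, assumed splits, and a simple signed-sum score, since the plan names no classifier. The conclusion did not change anywhere in those ranges. The claim in 7.1 is not supported by the planned analysis. The primary endpoint and the descriptive clinical results stand.

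**What to change.** 1. In 7.1 and 7.2, call the signatures hypothesis-generating, and label any correlation or separation shown in the derivation samples as descriptive.
2. If predictive performance is reported, take it only from patient-level cross-validation. Repeat gene selection and PCA in each fold, leave out all samples of a patient together, and give a label-permutation p value for the whole pipeline. State that leave-one-out is imprecise and biased downward at n = 12.
3. Replace survival as the prediction target with response measures the plan already names (lesion mCAILS response; patient-level PGA of skin at week 16), and state which signature is tested against which.

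The cost is a few sentences and a little computing. Reported performance will look less favourable and will be imprecise. No subjects, visits or samples are added.
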